All participants who permanently discontinue study drug should continue scheduled study visits. If the participant declines continued onsite visits but is agreeable to telephone calls, he/she will be contacted by the Investigator periodically to assess occurrence of CV events until death, documented withdrawal of participant informed consent (in writing if allowed by local regulations), or the final closure of the study.

The Investigator should show due diligence and explore all possible options to reach a participant who fails to return for a visit. In the case of participants lost to follow-up, attempts to contact the participant must be made and documented in the participant's medical records and in source documents. Per routine, in order to avoid participants lost to follow-up, the Investigator should ask the participant at the study start for the contact details of a relative or friend who can be contacted for participant contact information in case the participant cannot be reached.

Participants should not be withdrawn from follow-up unless they explicitly withdraw consent to be contacted. All efforts should therefore be made to minimize the number of participants who withdraw consent as, in general, no further information on CV events and survival status may be collected after that point. Participants who do not want regular in-person follow-up after cessation of study drug should be offered alternative methods of follow-up, including periodic telephone follow-up, contact at study closure, or assessment of health status via treating physicians or medical records. Such participants would then not be viewed as withdrawal of consent. The Investigator must explain to the participant all options for continued participation, and document which options were refused by the participant and the reason for refusal. Withdrawal of consent to all follow-up must be ascertained and documented in writing by the Investigator, who must inform the Sponsor and document the withdrawal of consent in the eCRF and medical records.

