## 9.2.1 Analysis of Efficacy

## 9.2.1.1 Primary efficacy analysis

The ITT Population will be the primary population for the efficacy analysis. Efficacy will also be analyzed using the FAS, mITT Population, and PP Population as supplementary analyses.

The primary efficacy endpoint is the percent change from Baseline to Day 84 in LDL-C in the obicetrapib group compared to the placebo group. The primary endpoint will be analyzed using an analysis of covariance (ANCOVA) model with a fixed effect for the treatment group and covariates of Baseline LDL-C, CV risk (HeFH or non-HeFH), and Baseline statin therapy (HIS or non-HIS). The least squares (LS) mean, standard errors, and 2-sided 95% confidence intervals for each treatment group and for the mean difference compared to placebo will be obtained. The model will be fit assuming unequal variances for each treatment group.

The primary estimand will correspond to a treatment policy estimand. The target population will comprise participants who are randomized into the study. The primary summary measure to assess the treatment effect will be the LS mean difference for the primary endpoint between obicetrapib

and placebo based on the ANCOVA methodology. The primary estimand will be addressed using the in-study observation period (ie, including data collected post-treatment discontinuation or post-prohibited medication use).

Missing data will be imputed for the primary efficacy analysis based on a pattern mixture model that uses a multiple imputation technique analyzed with ANCOVA with pre-specified fixed factors and covariates. If appropriate, based on the number of retrieved dropouts, missing measurements of non-retrieved dropouts will be modeled by known measurements from retrieved dropouts (ie, participants who remain in the study after treatment discontinuation) in the same treatment group. The imputation model will be further clarified in the SAP.

Additional sensitivity analyses may be carried out under secondary estimands and/or various assumptions for missing data. Full details will be provided in the SAP.

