3.1.2 Analysis Visits

Scheduled visits will be assigned to analysis visits as recorded on the CRF.

For each analysis visit, if a scheduled visit occurs within the analysis day window, then the measurement from this scheduled visit will be used. If no scheduled visit occurs or laboratory results of the scheduled visit were unreportable, the unscheduled measurement closest to the target day will be used. If measurements are equidistant to the target day, the later measurement will be used. Otherwise, unscheduled visits will not be re-assigned and will remain labelled as unscheduled. If laboratory measurements for the scheduled visit were taken while a participant was not in a fasting state and laboratory measurements are available from an unscheduled visit

during which the participant was in a fasting state (and the visit occurred within seven days of the scheduled visit), those fasted labs will be utilized in place of the unfasted labs.

Early termination (ET) visits will be assigned to analysis visits according to the visit windows in Table 2 and Table 3.

Table 2 Analysis Visit Windows (excluding Japan)

Analysis Visit	Target Analysis Day	Low Analysis Day	High Analysis Day
Day 1 (Visit 2)	1	NA	NA
Day 30 (Visit 3)	30	2	57
Day 84 (Visit 4)	84	58	132
Day 180 (Visit 5)	180	133	225
Day 270 (Visit 6)	270	226	317
Day 365 (EOT/Visit 7)	365	318	N/A

Table 3 Analysis Visit Windows (Japan Only)

Analysis Visit	Target Analysis Day	Low Analysis Day	High Analysis Day
Day 1 (Visit 2)	1	NA	NA
Day 14 (Visit 3)	14	2	22
Day 30 (Visit 4)	30	23	57
Day 84 (Visit 5)	84	58	132
Day 180 (Visit 6)	180	133	225
Day 270 (Visit 7)	270	226	317
Day 365 (EOT/Visit 8)	365	318	N/A

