3.4.1 Primary Efficacy Endpoints

Primary Analysis

The primary efficacy endpoint is the percentage change from Baseline to Day 84 in LDL-C in the obicetrapib group compared to placebo group.

The LDL-C values measured by preparative ultracentrifugation (PUC) will be used. If the later is not available, the LDL-C values will be assumed missing.

All the analysis for primary efficacy endpoint will be repeated with LDL-C values calculated as follows:

1. LDL-C will be calculated using the Friedewald equation unless triglycerides ≥ 400 mg/dL or LDL-C ≤ 50 mg/dL; where, LDL-C level will be measured directly by PUC.
2. LDL-C will be calculated using the Martin-Hopkins equation unless triglycerides ≥ 400 mg/dL or LDL-C ≤ 50 mg/dL; where, LDL-C level will be measured directly by PUC.

Primary Estimand

To assess the primary efficacy endpoint, the primary estimand is defined by the following key attributes:

- **Treatment:** obicetrapib versus placebo
- **Target Population:** participants who are randomized into the study
- **Analysis Population:** The ITT Population
- **Intercurrent events:** treatment discontinuation, prohibited medication use
- **Analysis set and handling of intercurrent events:** Treatment policy strategy will be used. All available values of LDL-C at Baseline and Day 84 will be included in the calculation of the percentage change from Baseline to Day 84.
- **Population level summary:** The difference in LS mean percentage change in LDL-C from Baseline to Day 84 between treatment groups

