The analysis of covariance (ANCOVA) model with a fixed effect for the treatment group and covariates of Baseline LDL-C, CV risk (HeFH or non-HeFH), and Baseline statin therapy (HIS or non-HIS) will be used to analyze the primary efficacy endpoint. The CV risk and Baseline statin therapy covariates, that were used in the stratification of the randomization scheme, will be classified according to the IRT stratification levels (meaning, the stratification categorization at the time of the randomization). The least squares (LS) mean, standard errors, and 2-sided 95% confidence intervals for each treatment group and for the mean difference compared to placebo will be estimated. The model will be fit assuming unequal variances for each treatment group. If substantial deviations from the model assumptions are observed, then supportive analyses, such as non-parametric assessments, will be considered. The primary efficacy analysis will be conducted based on the ITT Population.

Missing data will be imputed for the primary efficacy analysis based on a pattern mixture model that uses a multiple imputation technique analyzed with ANCOVA with pre-specified fixed factors and covariates. If appropriate, based on the number of retrieved dropouts, missing measurements of non-retrieved dropouts will be modeled by known measurements from retrieved dropouts (ie, participants who remain in the study after treatment discontinuation) in the same treatment group. If the number of retrieved dropouts is such that the model convergence is questionable and the

given parameter estimates cannot be obtained, then missing data at the Day 84 assessment will be estimated based on the placebo treatment group as described in subsequent sections of the SAP corresponding to the first sensitivity analysis.

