Missing data at Day 84 will be imputed using a retrieved dropout imputation model assuming the data are missing not at random (MNAR). At Day 84, the data will be split into two groups as follows: (1) all participants that did not discontinue treatment and had a non-missing value at Day 84; and (2) either participants that had a missing value at Day 84, or participants that had discontinued treatment and had a non-missing value at Day 84. For the second group, 100 data sets will be imputed. The variables for the imputation model will consist of the LDL-C values from Baseline and Day 84, along with treatment group, CV risk (HeFH or non-HeFH) and Baseline statin therapy (HIS or non-HIS). Each data set will be combined with the first group to obtain 100 imputed data sets with no missing values at Day 84. For each imputation data set, the percent change from baseline to Day 84 will be analyzed using the ANCOVA model described above. The results of these 100 analyses will be combined to construct the treatment estimates using the parameter estimates and associated standard errors. Similarly, the difference of the adjusted treatment means (obicetrapib vs. placebo) will be presented with the associated standard error and two-sided 95% confidence interval. Randomly chosen seed numbers will be selected for the analysis and will be retained.

Sample SAS code is shown below:

1.1

```
*****
Note: Missing value imputation only using participant group (2): participants that had a
missing value at Day 84, or participants that had discontinued treatment and had a non-
missing value at Day 84
```

TREATMENT = 0 (Placebo), 1 (Obicetrapib)

LDLC_BASE = Baseline LDL_C value

LDLC_Day84 = LDL_C value at Day 84

CVRISK = 1 (HeFH), 0 (non-HeFH)

STATIN = 1 (HIS), 0 (non-HIS)

```
*****
proc mi data=LDL_C seed=8267356 n impute=100 out= LDL_C_IMP;
class TREATMENT CVRISK STATIN;
monotone method=reg;
var TREATMENT CVRISK STATIN LDLC_BASE LDLC_DAY84;
run;
```

1.2

```
*****
Note: LDL_C_IMP dataset must be merged with dataset containing participants from
group (1): participants that did not discontinue treatment and had a non-missing value at
Day 84.
```

Note: For each imputation dataset, the percentage change from Baseline to Day 84 will be analyzed using an ANCOVA approach with a fixed effect for the treatment group and covariates of Baseline LDL-C, CV risk (HeFH or non-HeFH), and Baseline statin therapy (HIS or non-HIS).

TREATMENT = 0 (Placebo), 1 (Obicetrapib)

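### SAP 3.4.1 imputes every missing Day 84 LDL-C from participants who stopped treatment, including those still on study drug, which can pull the primary estimate toward placebo

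*SAP*

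**What the plan says.** **Whom the imputation covers.** The narrative in SAP 3.4.1 gives this rule, applied within each arm: "missing measurements of non-retrieved dropouts will be modeled by known measurements from retrieved dropouts (ie, participants who remain in the study after treatment discontinuation". Protocol 9.2.1.1 has the same rule ("missing measurements of non-retrieved dropouts will be modeled by known measurements from retrieved dropouts") and leaves the details to the SAP. The operational paragraph of SAP 3.4.1 then splits the data in two. Group 1 is everyone still on treatment with an observed value. Group 2 is "either participants that had a missing value at Day 84, or participants that had discontinued treatment and had a non-missing value at Day 84". Only group 2 enters the imputation model, and the SAS note repeats this. The model contains treatment arm, the two stratification factors and LDL-C at Baseline and Day 84. It has no term for treatment status.

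**When a value counts as missing.** The primary analysis uses ultracentrifugation values only: "If the later is not available, the LDL-C values will be assumed missing". SAP 3.1.2 allows some substitution: "If no scheduled visit occurs or laboratory results of the scheduled visit were unreportable, the unscheduled measurement closest to the target day" is used instead.

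**The estimand.** It is treatment policy: "All available values of LDL-C at Baseline and Day 84 will be included".

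**Stopping-visit samples.** Under SAP 3.1.2, "Early termination (ET) visits will be assigned to analysis visits according to the visit windows in Table 2 and Table 3"; the Day 84 window is Days 58 to 132. Protocol 4.3 makes an onsite visit at which a participant stops drug and declines further participation the ET visit. Protocol 7.1 measures LDL-C by ultracentrifugation there. Protocol 4.3 also says: "All participants who permanently discontinue study drug should continue scheduled study visits".

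**The concern.** A participant can be on study drug and still lack a Day 84 value: a visit missed or held virtually (Protocol 3.1.1, SAP 3.1.3), or no ultracentrifugation result. The unscheduled-sample rule reduces such cases but does not remove them. Under the treatment-policy estimand this participant's value is an on-drug value. The operational rule puts the participant in group 2, where the only observed Day 84 values belong to people who discontinued. If the effect wanes off drug, the imputed obicetrapib values are too high and the treatment difference shrinks.

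A secondary question concerns the donors. The group 2 wording neither repeats the narrative's condition that donors remain in the study nor dates discontinuation relative to the Day 84 sample. Read literally, a sample drawn at the visit where drug is stopped could serve as an off-treatment donor value. That would push the estimate away from placebo if the recipients are truly off drug.

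At stake is the size of the primary effect and its CI. Programmers following the narrative and the operational paragraph could report different ones.

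**Working it through.** **1. The plan's own figures (SAP 2.2.2).** 2400 × 0.95 = 2280 evaluable; at 2:1 that is 1520 and 760. With SD 15, SE = 15 × √(1/1520 + 1/760) = 0.67, and 0.65 with all 2400, so about 0.66. The 95% CI half-width is 1.27 to 1.31 points. A 30-point difference is about 45 SEs, so power is effectively 100%, consistent with the stated figure of more than 90%.

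**2. Recipients and donors side by side.**

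| | Narrative (SAP 3.4.1, Protocol 9.2.1.1) | Operational text and SAS note (SAP 3.4.1) |
|---|---|---|
| Recipients | Non-retrieved dropouts | Anyone missing Day 84, on or off drug |
| Donors | Discontinued and still in the study | Discontinued, with a Day 84 value |
| Observed on-treatment participants | Not mentioned | Outside the imputation |

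**3. Bias from on-drug recipients.** Let m be the share missing Day 84, q the share of the missing still on drug, and D the effect lost off drug. Their true mean is D points lower than the donors', so the obicetrapib mean shifts by D × m × q. No shift is expected in placebo. D = 30 is the plan's effect, assumed fully lost off drug; if half is lost, every bias halves. The values of q are assumed. The 5% for m is the plan's approximate drop-out rate, not a cap and not specific to Day 84.

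The rule was simulated with 1600 and 800 participants, donors 2% of each arm (32 and 16), and baseline mean 100, SD 25, floored at 55 mg/dL. There were 500 replicates with 20 imputations, Rubin pooling and unequal variances; stratification factors were left out. Monte Carlo error is about 0.03 for bias and 1 to 1.6 points for coverage. Positive means toward placebo. The last column imputes on-drug gaps from on-drug participants.

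| m | q | 30 × m × q | Simulated bias | Coverage, SAP rule | Coverage, split rule |
|---|---|---|---|---|---|
| 1% | 0.5 | 0.15 | +0.15 | 94% | 96% |
| 2.5% | 0.25 | 0.19 | +0.20 | 95% | 95% |
| 2.5% | 0.5 | 0.375 | +0.39 | 91% | 95% |
| 5% | 0.25 | 0.375 | +0.41 | 94% | 94% |
| 5% | 0.5 | 0.75 | +0.76 | 85% | 97% |

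Repeat runs, some with other baseline and donor assumptions, gave +0.35 at m = 2.5%, q = 0.5, and +0.74 to +0.80 at m = 5%, q = 0.5. Imputing on-drug gaps from on-drug participants brought both settings within 0.1 point of zero.

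**4. The donor ambiguity.** Let w be the share of donors sampled while still on drug (assumed). The combined bias is 30 × m × (q − w). With q = 0 and m = 5%, w = 0.25 gives −0.375 (simulated −0.37) and w = 0.5 gives −0.75 (simulated −0.80). With q = w = 0.5 the two cancel (simulated −0.02).

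**5. Would a minimum off-drug interval for donors help?** Let half of the donors and half of the off-drug recipients be recent stoppers who keep the effect, with m = 5% and q = 0. The SAP rule is then nearly unbiased (+0.02; −0.07 in a repeat). Excluding recent stoppers from the donors alone leaves recent-stopper recipients imputed from people long off drug: 30 × 0.05 × 0.5 = 0.75 expected, +0.82 simulated (+0.75 in a repeat).

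**The case against.** **The texts do not flatly contradict each other.** The protocol defers the imputation model to the SAP. The SAP narrative opens with missing data in general, and its placebo-based fallback covers all missing Day 84 values. The operational paragraph may simply fill a gap. That is fair, but it fills the gap by treating on-drug participants as discontinuers, gives no reason, and SAP Section 6 does not list the wider scope as a change.

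**Donor contamination is not shown.** A reader might infer that on-drug samples will serve as off-drug donors. The documents do not support that. The narrative defines retrieved dropouts as people who stay in the study, which excludes ET visits of those who decline further participation. Having discontinued at Day 84 can also be read as having stopped before the sample. This part is an ambiguity, and one sentence would settle it.

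**The sizes rest on assumptions.** Neither q, w, the donor share nor the loss of effect off drug is in the documents. Taking half of a drop-out figure as still on drug is an upper illustration, and several of the coverage contrasts are within Monte Carlo error.

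**Other analyses would show a divergence.** The observed-case and tipping-point analyses and the MMRM do not use the group 2 rule. They can reveal a difference but do not correct the primary estimate.

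**Conclusion.** The mismatch over recipients stands. Followed literally, the operational rule imputes on-drug participants from discontinuers, which does not fit the treatment-policy estimand and biases the primary estimate toward placebo by about 30 × m × q. Under the stated assumptions this is about +0.35 to +0.4 points at m = 2.5%, q = 0.5 and about +0.75 at m = 5%, q = 0.5, against an SE of about 0.66. At lower m or q it is a few tenths of a point or less.

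Two stronger conclusions should not be drawn. The superiority test is not in doubt, because shifts of this size are trivial beside 30 points. Nor is the net direction known if the donor ambiguity is also resolved the wrong way, since the two effects oppose each other and may cancel. The point concerns the reported effect size and its CI, and should be settled before unblinding.

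**What to change.** Make the SAP 3.4.1 narrative, operational paragraph and SAS note agree with each other and with Protocol 9.2.1.1, by treatment status at Day 84:

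- **(a) On treatment, value missing:** impute from observed on-treatment participants of the same arm, with the covariates already listed.
- **(b) Off treatment, value missing:** impute from retrieved dropouts as the narrative defines them (still in the study), with discontinuation dated before the Day 84 sample. State how interruptions and restarts are classed. Use the recorded discontinuation date: a last-dose rule could still admit someone who stops at Visit 4, and with (a) in place it gave −0.41 at m = 5%, q = w = 0.5. Do not add a minimum off-drug interval for donors unless recipients are matched on time since stopping, through a time-off-drug term or the same condition on recipients.
- **(c) Observed values:** keep every value mapped to Day 84, including ET samples, as that participant's own treatment-policy value.

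Keep the existing placebo-based fallback. The cost is SAP wording and modest programming, with no new data. There may be slightly fewer donors and a slightly larger SE: dropping stopping-visit samples when they are half the donors gave 0.81 against 0.80 (m = 5%, q = 0).

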## 7.1 Lipid Profile/Biomarkers

Samples will be collected for the lipid profile/biomarkers at visits specified in the Schedule of Procedures (Appendix A). The lipid profile/biomarker samples will be analyzed for ApoB, HDL-C, LDL-C, non-HDL-C, TC, and TG. Samples should be collected while the participant is fasting (a minimum of 8 hours).

At Baseline (Visit 2), Day 84 (Visit 4), and Day 365 (Visit 7)/EOT/ET, LDL-C will be measured for all participants by preparative ultracentrifugation, also referred to as beta quantification. At all other scheduled visits, LDL-C will be calculated using the Friedewald equation unless TG  $\geq$ 400 mg/dL ( $\geq$ 4.5 mmol/L) or LDL-C  $\leq$ 50 mg/dL ( $\leq$ 1.3 mmol/L). If TG  $\geq$ 400 mg/dL ( $\leq$ 4.5 mmol/L) or LDL-C  $\leq$ 50 mg/dL ( $\leq$ 1.3 mmol/L), then LDL-C level will be measured directly by preparative ultracentrifugation.

All lipid profile/biomarker values will be blinded during the study through the EOS Visit (Visit 8). Participants, the Sponsor, Investigators, and all study site personnel involved in the study, including personnel carrying out study procedures, evaluating participants, entering study data, and/or evaluating study data, will remain blinded to lipid profile/biomarker values until all participants have completed the EOS Visit and the database has been locked for analysis.

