Supplemental analyses will be performed for the primary efficacy endpoint in order to assess any differences with the results from the primary analysis and investigate what effect, if any, protocol violations have on the trial results. In the first supplemental analysis, a mixed model for repeated measures (MMRM) approach will be utilized. The LDL-C values measured by preparative ultracentrifugation will be used. The analysis will include fixed effects for treatment group, visit, and treatment-by-visit interaction, along with covariates of the Baseline LDL-C value as a continuous covariate, CV risk (HeFH or non-HeFH), Baseline statin therapy (HIS or non-HIS). The restricted maximum likelihood estimation approach will be used with an unstructured covariance matrix. The LS mean, standard errors, and 2-sided 95% confidence intervals for the treatment group and for the comparison of the treatment group to the placebo group will be provided. The MMRM approach will include all available assessments of percent change in LDL-C from Day 1, Day 30, Day 84, Day 180, Day 270, and Day 365. The model assumes that the data are missing at random (MAR). If any data are missing, the model will use all information from the other time points to estimate the mean treatment difference at the given time point. No imputation of missing data will be performed. The analysis will be conducted for ITT Population.

The analysis will be implemented using SAS® Proc Mixed. The sample SAS code can be found below:

Note:

USUBJID = unique subject identifier
TREATMENT = 0 (Placebo), 1 (Obicetrapib)
VISIT = visit
LDLC_BASE = Baseline LDL_C value
PCHG = Percent change from Baseline
CVRISK = 1 (HeFH), 0 (non-HeFH)
STATIN = 1 (HIS), 0 (non-HIS)

```
proc mixed;
  class USUBJID TREATMENT VISIT CVRISK STATIN;
  model PCHG = TREATMENT LDLC_BASE CVRISK STATIN VISIT TREATMENT*VISIT / solution cl;
  Repeated VISIT / TYPE=UN sub=USUBJID;
  lsmeans VISIT*TREATMENT / cl diff;
```

run;

Additional supplementary analysis will be performed using the ANCOVA model from the primary analysis based on the FAS, MITT, MITT On Treatment, and PP populations. No imputation for missing data will be performed for the analysis.

Secondary Estimand

A secondary estimand will be assessed for the primary efficacy endpoint. The secondary estimand is defined by the following key attributes:

- **Treatment:** obicetrapib versus placebo
- **Target Population:** participants who are randomized into the study

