3.4.2 Secondary Efficacy Endpoints

Similar ANCOVA models as described for the primary analyses will be used to analyze the secondary efficacy endpoints and will be tested sequentially at the 0.05 significant level according to the order specified below:

- Percentage change from Baseline to Days 30, 180, 270 and 365 in LDL-C in the obicetrapib group compared to the placebo group;
- Percentage change from Baseline to Days 84, 180, and 365 in ApoB in the obicetrapib group compared to placebo group;
- Percentage change from Baseline to Days 84, 180, and 365 in non-HDL-C in the obicetrapib group compared to placebo group;
- Percentage change from Baseline to Days 84, 180, and 365 in HDL-C in the obicetrapib group compared to placebo group;
- Percentage change from Baseline to Days 84 in Lp(a) and ApoA1 in the obicetrapib group compared to placebo group;

- Percentage change from Baseline to Days 84, 180, and 365 in TC in the obicetrapib group compared to placebo group;
- Percentage change from Baseline to Days 84, 180, and 365 in TG in the obicetrapib group compared to placebo group.

For the percentage change from Baseline to Day 30, 180 and 270 in LDL-C, the LDL-C will be calculated using the Friedewald equation unless the Triglyceride value is ≥ 400 mg/dL or the LDL-C value is ≤ 50 mg/dL; in which case, the LDL-C level measured directly by PUC will be used in the analysis. The latter approach will be used because PUC assessments are not performed at Day 30, 180 and 270 as per the protocol, unless the conditions for Triglycerides or LDL-C described above are met at the Day 30, 180 and 270 assessments. The analysis will be repeated using the Martin-Hopkins equation as described in the [Section 3.4.1](#) above.

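### The PUC-only MMRM in SAP 3.4.1 includes three visits where PUC is run only if that visit's own lipid values trigger it, so MAR fails and the LS means at Days 30, 180 and 270 are biased

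*SAP*

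**What the plan says.** SAP 3.4.1 (Supplemental Analyses) defines an MMRM for percentage change in LDL-C in the ITT Population, under MAR and without imputation. On the assay: "The LDL-C values measured by preparative ultracentrifugation will be used". On the visits, the model "will include all available assessments of percent change in LDL-C from Day 1, Day 30, Day 84, Day 180, Day 270, and Day 365". On missing values, "the model will use all information from the other time points to estimate the mean treatment difference at the given time point". The terms are treatment, visit, their interaction, Baseline LDL-C, CV risk and statin stratum. The sample code requests LS means for every visit and arm.

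SAP 3.4.1 (Secondary Estimand) handles the hypothetical estimand with a model described as similar to this one. Its narrative treats values after discontinuation or prohibited medication as missing. It names no assay.

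Protocol 7.1 schedules PUC for everyone only at Baseline, Day 84 and Day 365/EOT/ET. "At all other scheduled visits, LDL-C will be calculated using the Friedewald equation unless TG" is at least 400 mg/dL or LDL-C is at most 50 mg/dL. SAP 3.4.2 agrees that "PUC assessments are not performed at Day 30, 180 and 270 as per the protocol, unless the conditions for Triglycerides or LDL-C" are met, and for that reason adopts a Friedewald/PUC rule, but only for the secondary-endpoint ANCOVAs. For the primary endpoint, SAP 3.4.1 treats LDL-C as missing when no PUC value exists. It also states: "All the analysis for primary efficacy endpoint will be repeated with LDL-C values calculated as follows", naming Friedewald and Martin-Hopkins versions with the same PUC override.

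**The concern.** At three of the five post-baseline visits, the chosen assay exists mainly for participants whose LDL-C was low or whose triglycerides were very high at that visit. The model sees neither quantity when PUC is absent. That selection is not ignorable, and it acts much more often on the arm whose LDL-C is lowered. The model would still print LS means and ordinary confidence intervals for those visits.

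The hypothetical estimand raises a second question. It removes values after discontinuation or prohibited medication and relies on other visits to recover Day 84. Day 30 is the only scheduled post-baseline visit before Day 84, and most of its PUC data would not exist.

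**Working it through.** **1. The plan's own figure.** SAP 2.2.2: 2400 x 0.95 = 2280 evaluable, or 1520 and 760 at 2:1. SE = 15 x sqrt(1/1520 + 1/760) = 0.67 and 30/0.67 = 45, so power is essentially 100%, consistent with the stated more than 90%. This is not in dispute; it supplies the effect (30%) and SD (15%) used below.

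**2. PUC by visit.**

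| Visit | PUC available (Protocol 7.1, SAP 3.4.2) | Response visit in the MMRM |
|---|---|---|
| Days 84, 365 | everyone | yes |
| Days 30, 180, 270 | only if triggered | yes |

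The exception is an ET visit, which has PUC (Protocol 4.3 and 7.1) and is mapped by SAP 3.1.2: Days 58-132 go to Day 84, and other ET visits can fall in the Day 30, 180 or 270 windows.

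**3. How often LDL-C alone triggers PUC.** With baseline B and percent change normal with mean m and SD 15, P(LDL-C <= 50) = Phi[(100 x (50/B - 1) - m)/15], where m is -30 on obicetrapib and 0 on placebo.

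| B (mg/dL) | Cut-off (% change) | Obicetrapib | Placebo |
|---|---|---|---|
| 70 | -28.6 | 54% | 3% |
| 80 | -37.5 | 31% | 0.6% |
| 100 | -50 | 9% | about 0% |

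Availability depends on the unobserved response and on arm, so MAR does not hold.

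**4. Effect at Days 30, 180 and 270 (simulation).** N = 2400, 2:1, true contrast -30 at every visit, SD 15, unstructured covariance, Day 1 left out. Assumed, not in the documents: baseline mean/SD 85/20, 100/30 or 120/35 mg/dL with a floor of 55; correlation 0.4 to 0.8; 1% with triglycerides of at least 400; Friedewald error SD 5 mg/dL; 5 to 20% missing at Day 84.

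- Share with a Day 30 PUC value: obicetrapib 12-35%, placebo 2-5%.
- Day 30 LS means: obicetrapib about -37 to -40 (truth -30), placebo about -7 to -12 (truth 0).
- Contrasts at the three visits: about -26 to -35.

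A second simulation (SD 15, baseline mean 85, SD 32) changed only the triglyceride trigger rate. At 0.5, 1, 2 and 4% the contrast was -26.6, -29.1, -31.8 and -33.4, so the error changes sign with an input the documents do not give.

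**5. Effect at Day 84.** In the first simulation, with 5-10% missing similarly in both arms, PUC-only and the fix below differed by less than 0.1 point. With 10% of the obicetrapib arm missing, concentrated in poor Day 30 responders, PUC-only gave -30.6 (observed cases -30.7) and the fix -30.0.

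The second simulation used effects of 30% and 50%, SDs of 15 and an assumed 25, baseline mean 98, 2% triglyceride triggers and correlation 0.65. Shifts against a model with PUC at every visit:

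| Response-dependent loss after Day 30 | Shift (points) | If half have an ET PUC in the Day 30 slot |
|---|---|---|
| none | 0.00 | - |
| 10% in both arms | -0.01 to +0.11 | +0.07 to +0.36 |
| 5% in obicetrapib only | -0.35 to -0.71 | - |
| 10% in obicetrapib only | -0.69 to -1.42 | -0.08 to -0.33 |

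The SE of the Day 84 estimate was 0.65 (SD 15) and 1.1 (SD 25).

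**6. Two wording points in the same text.** Day 1 is listed as a response visit, but percent change there is 0 for everyone, so its variance in an unstructured covariance is degenerate. The handling bullet of the hypothetical estimand repeats the treatment-policy sentence of the primary estimand, while its narrative excludes post-event values.

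**The case against.** The strongest reply concerns weight. The supplemental MMRM is an ITT analysis of all available values, Protocol 4.3 keeps participants who stop drug on scheduled visits, and everyone has PUC at Day 84. Stopping drug therefore does not remove the Day 84 value; only study dropout does, planned at about 5%. An ET visit on Days 58-132 itself fills the Day 84 slot. A reader might infer that the supplemental Day 84 contrast is materially wrong. The documents do not support that, and this part of the reply stands.

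For the hypothetical estimand, the larger shifts need losses in one arm driven by Day 30 response. Lipid values are blinded (Protocol 7.1). The pre-Day 84 alert in Protocol 8.8.3 requires both LDL-C above 200 mg/dL and a rise of more than 50%, and it is accompanied by sham alerts; it would mostly reach placebo. Indirect routes such as non-adherence remain possible, but the documents give little mechanism. This also stands.

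The planned repeats mitigate in part. Both models are presented as analyses of the primary endpoint ("Supplemental analyses will be performed for the primary efficacy endpoint in order to assess any differences with the results from the primary analysis"; "A secondary estimand will be assessed for the primary efficacy endpoint"), so the Friedewald and Martin-Hopkins repeats cover them and are fully populated. They replace PUC at Baseline and Day 84 too, except where triggered. A reader might call the absence of an MMRM with PUC at Day 84 and full Day 30 data an error. No document requires one; it is a limitation.

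Finally, the three visits' LS means are by-products here, since SAP 3.4.2 supplies the tested ones, and the bias sizes rest on assumed distributions with Day 1 removed. Both points are true, but neither rescues MAR at those visits, which fails by design.

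**Conclusion.** The specification is wrong as written, with limited reach. MAR fails at Days 30, 180 and 270, and the PUC-only LS means and contrasts there should not be relied on. At SD 15 and a true -30, the first simulation's contrasts were about -26 to -35. Size and sign depend on baseline LDL-C and triglyceride distributions that the documents do not give, so the error cannot be called conservative.

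The supplemental Day 84 contrast is little affected. The hypothetical-estimand MMRM loses most of its Day 30 support; its Day 84 estimate shifts by roughly 0.4 to 1.4 points only if exclusion is response-dependent and confined to obicetrapib, and by less if ET PUC values are available. Blinding makes that unlikely.

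A reader might extend the problem to the main efficacy result. That does not follow: the primary imputation and ANCOVA use only Baseline and Day 84, and the tested Day 30, 180 and 270 ANCOVAs already use the Friedewald/PUC rule.

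**What to change.** In both MMRMs, use PUC at Baseline, Day 84 and Day 365, and the SAP 3.4.2 Friedewald/PUC rule at Days 30, 180 and 270. Take percent change at those three visits from a Baseline derived by the same rule, and keep the PUC Baseline as the single Baseline covariate. Name the assay in the Secondary Estimand text. At minimum, do not report LS means at those three visits from the PUC-only model. Dropping the visits removes the biased estimates but does not restore Day 30 support for the hypothetical estimand.

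Keep the Friedewald and Martin-Hopkins repeats as sensitivity analyses. Remove Day 1 as a response visit. Reword the hypothetical handling bullet to exclude values after treatment discontinuation or prohibited medication, as its narrative says.

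The cost is SAP wording and a changed analysis variable at three visits. No new data are needed, because the planned repeats already require a Friedewald Baseline. The drawback is mixed assays across visits. With an assumed Friedewald error of mean -4 and SD 6 mg/dL, the matched Baseline cut the error in the visit contrasts from 1.4-3.0 points to 0.2-1.0, and the Day 84 shift under 10% obicetrapib-only loss was -0.07 to -0.21.
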